#### 7.2. DEMOGRAPHIC AND OTHER BASELINE CHARACTERISTICS

Demography (gender, race, ethnicity, age [years], weight [kg], height [cm] and BMI [kg/m²]) will be summarised overall and by treatment group for the FAS. Age, weight, height and BMI will be summarised using summary statistics for continuous variables. Gender, race, ethnicity and Fitzpatrick Skin Type Classification will be summarised using summary statistics for categorical variables.

Age = (Day 1 date - date of birth + 1)/365.25 truncated to complete years.

For Cohorts 2 and 3, the following baseline characteristics will be summarised using descriptive statistics by treatment group and overall, for subjects in the FAS; except for EASI (categorical), VRS and IGA which will present counts and percentages:

- Duration of atopic dermatitis (years)
- EASI
- EASI (categorical): ≤20 and >20
- % BSA Affected
- IGA score
- NRS for worst pruritus (over 24 hours)\*
- duration of itching (over 24 hours)\*
- NRS for sleep disturbance\*
- VRS for pruritus (over 24 hours)\*

Duration of atopic dermatitis in years will be calculated from the date of onset recorded on medical history relative to Day 1 i.e. Day 1 date - onset date divided by 365.25.

SAP Version v2.0 Page 26 of 43

\* Only summarised for Cohort 3.

Date: 16th March 2017

#### 7.3. MEDICAL HISTORY AND CONCOMITANT DISEASES

Medical history will be coded using the latest Medical Dictionary for Regulatory Activities (MedDRA) Version available. Summaries will be presented for the FAS by System Organ Class (SOC) and Preferred Term (PT) with counts and percentages for each treatment group and overall. Each subject will be counted only once in each SOC or SOC/PT summary.

### 7.4. PRIOR AND CONCOMITANT MEDICATIONS

Prior and concomitant medications will be coded using the latest WHO Drug Dictionary version available. Medication will be presented for the safety population by ATC level 2 (therapeutic main group) and ATC level 5 (standardized medication name) with counts and percentages for each treatment group and overall. A subject who took more than one medication will be counted only once if these medications belong to the same extended ATC classification.

In addition, a summary of prior emollients (excluding study emollients) and concomitant emollients will be presented for Cohorts 2 and 3 with counts and percentages for each treatment group. Prior emollients will exclude study emollients which will be identified as emollients started prior to dosing but on or after the screening visit. The study emollients used were for Cohort 2 and for Epaderm for Cohort 3. A clinical review of all unique medications will be done prior to database lock to identify emollients.

Prior medications will be defined as those medications started prior to the administration of study drug on Day 1. Concomitant medications will be defined as those medications taken following the first administration of study drug on Day 1. Hence medications started before study dosing, but continuing after are considered as both prior and concomitant medications. The listing of medications will identify prior and concomitant medications.

If either the start or stop date of medication is missing, the worst or most conservative case will be considered when assigning medications to categories. So for a missing start date (where stop date is after date of first dose) the date will be imputed as the date of first dose; for a missing stop date the date will be imputed as the subject's last study day or start date if start date is after last dose. If a partial date is recorded, the following convention will be used to assign the medication:

- If a partial date is missing a start day and the month/year is the same as first dose date then use first dose date, else '01' will be used for the day; if a start date is missing a month and the year is the same as first dose date then use first dose date, else January will be used for the start month.
- If a partial date is missing a stop day and month/year is same as last study date then use last study date, else last day of the given month will be used for the stop day; if a stop date is missing a month and the year is the same as last study date then use last study date, else December will be used for the stop month.

SAP Version v2.0 Page 27 of 43

Date: 16th March 2017

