#### 5.7. PROTOCOL DEVIATIONS

All protocol deviations will be reviewed and documented before database lock. Protocol deviations will be recorded by the site staff, study monitors and medical monitor reviewers. They may also be identified through programmable checks of the data.

Key protocol deviations include:

- Violations of inclusion and exclusion criteria. This includes unknown violations at enrolment and on-study violations, like taking a prohibited medication
- Poor IMP compliance
- Subject receiving the incorrect IMP

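### SAP 7.4's partial-start-date rule ignores the recorded stop date, so a medication stopped before Day 1 can be given a start after its own stop and lose its prior status

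*SAP*

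**What the plan says.** SAP 7.4 opens its date conventions with a general principle: "the worst or most conservative case will be considered when assigning medications to categories". It then gives two separate rules for start dates.

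- **Start wholly missing.** The first-dose date is used, but only under a condition on the stop date: "missing start date (where stop date is after date of first dose) the date will be imputed as the date of first dose".
- **Start partly known.** A new convention begins: "If a partial date is recorded, the following convention will be used to assign the medication". With the day missing: "If a partial date is missing a start day and the month/year is the same as first dose date then use first dose date". With the month missing: "if a start date is missing a month and the year is the same as first dose date then use first dose date". If the known month or year differs from that of first dose, the first of the month or January is used. The stop date is not mentioned.

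The same section sets the categories. "Prior medications will be defined as those medications started prior to the administration of study drug on Day 1", so prior status depends on the start date alone. Concomitant means taken after the first administration on Day 1. Protocol 5.11 defines prior more simply, as anything taken before dosing began, and has start and stop dates recorded in the case report form.

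**The concern.** The guard on wholly missing dates stops the first-dose date being assigned to a drug already known to have stopped. The partial-date convention lacks that guard, so a record carrying more information can receive an impossible date: a start later than its own recorded stop.

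In this trial a stop before Day 1 is the designed pattern. Cohort 2 and 3 patients give up their usual emollient at least 7 days before Day 1 (Protocol 4.2, SAP 3.5), and listed AD therapies are washed out over 1 week to 1 month (Cohort 2 and 3 schedules; Protocol Table 6). These are the records that the prior medication table (14.1.4.1) and the prior emollient table (14.1.4.3.1) exist to describe. If they appeared as concomitant instead (14.1.4.2, 14.1.4.3.2), a washed-out steroid would read as on-study use of a prohibited therapy, in a trial that provides no rescue medication.

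**Working it through.** The plan states no figure on this point, so the check is to apply the written rule to example records. The first-dose date of 20 October 2016 is an assumption. The stop dates are 7, 8 and 28 days before it, in line with the emollient switch and the washout range.

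Rule as written: a year-only start in the first-dose year, or a month/year start in the first-dose month, becomes the first-dose date. Any other partial start becomes 1 January or the first of the month. Prior = start before first dose.

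| Record | Recorded start | Recorded stop | Start under SAP 7.4 | Start minus stop | Prior? |
|---|---|---|---|---|---|
| Topical steroid or usual emollient | 2016 | 13 Oct 2016 | 20 Oct 2016 | +7 days | No |
| Topical calcineurin inhibitor | Oct 2016 | 12 Oct 2016 | 20 Oct 2016 | +8 days | No |
| Systemic steroid | 2016 | 22 Sep 2016 | 20 Oct 2016 | +28 days | No |
| Any | Aug 2016 | 12 Oct 2016 | 1 Aug 2016 | −72 days | Yes |
| Any | 2015 | 13 Oct 2016 | 1 Jan 2015 | −651 days | Yes |

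The first three rows are impossible dates and lose prior status. Their concomitant status depends on the program:

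- if it follows the imputed start (on first dose), the record is concomitant;
- if it follows the recorded stop (before first dose), the record is not concomitant and belongs to neither category.

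The last two rows are classed correctly, which marks the limit of the problem.

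With the stop-date guard added, the first and third rows start on 1 January 2016 and the second on 1 October 2016. Each start precedes its stop, and all three are prior only. A medication still ongoing at first dose is unaffected by the guard.

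**How often, given a partial start?** This can only be illustrated. Assume Day 1 is uniform from August 2016 to January 2017, the stop is 7 to 28 days earlier, and the start is uniform over a window before the stop. The share of records caught by simulation is:

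| Start window before stop | Year-only starts | Month/year starts |
|---|---|---|
| 3 months | 84% | 4% |
| 6 months | 84% | 2% |
| 1 year | 62% | 1% |
| 2 years | 31% | under 1% |
| 5 years | 12% | under 1% |
| 10 years | 6% | under 1% |

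The range is wide because long-standing therapies usually began in an earlier year, which the rule handles correctly. The assumed Day 1 window does not represent Cohort 2, which had already reported emollient reactions when Protocol version 2.0 was dated 28 July 2016.

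**The case against.** The best defence is that this is a small drafting gap with safeguards around it. Concomitant means taken after first dose, so a record with a stop before Day 1 does not meet that definition whatever its imputed start. SAP 6.2 keeps raw data in the listings and marks imputed values, so a reader can see the true stop. SAP 5.4 and 5.7 have deviations and Per Protocol exclusions reviewed and documented before database lock. Complete dates, and partial dates in earlier months or years, are classed correctly.

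All of that stands, and it rules out three stronger readings that a reader might infer.

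- *Washed-out therapies will be tabulated as concomitant.* The text does not force this. It is plausible, because the convention is there to assign the medication and the section favours the conservative case, but the alternative is that the record falls in neither category.
- *Patients will be wrongly removed from the Per Protocol set.* SAP 5.7 lists on-study prohibited medication as a key deviation and says of deviations "They may also be identified through programmable checks of the data". It does not say that such checks use imputed dates. A false exclusion would need that, and a pre-lock review that missed the recorded stop.
- *Ongoing medications with a year-only start also wrongly lose prior status.* A start known only to lie in the first-dose year does not establish use before Day 1. Treating it as starting at first dose is the SAP's stated conservative convention and matches its rule for wholly missing starts.

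The safeguards do not repair the summary tables. A start after the recorded stop is not conservative, and the loss of prior status follows directly from the SAP's own definition and contradicts Protocol 5.11.

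**Conclusion.** The rule is wrong as written, within a narrow scope. It reaches medications with a year-only start in the first-dose year, or a month/year start in the first-dose month, and a recorded stop before Day 1. Each gets a start after its stop and drops out of the prior tables; its concomitant status is then either wrong or empty, depending on the program.

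The consequence is confined to Tables 14.1.4.1, 14.1.4.2, 14.1.4.3.1 and 14.1.4.3.2 and the prior/concomitant flags in the medication listing. The primary EASI analysis on the FAS does not use these categories. An effect on the Per Protocol sensitivity analysis is possible only under the conditions described above. The number of affected records is unknown: the documents do not say how often start dates are partial, and the simulated shares apply only to records that are partial, under assumed dates.

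**What to change.** In the partial-start bullet of SAP 7.4, add the stop-date condition: use the first-dose date only if the stop date is missing, ongoing, or on or after first dose. Otherwise use the first day of the known month, or January where the month is unknown, and never a date after the recorded stop. Medications with a recorded stop before first dose are then classed as prior only. It would also help to say that the concomitant flag respects the recorded stop date.

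The cost is one sentence in the SAP and about one line of code before database lock. No new data are needed, and no efficacy model changes.

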### 8. EFFICACY

As Cohort 1 includes healthy volunteers no efficacy data will be collected. Though some efficacy assessments are included for Cohort 2 the data will only be listed and no formal comparisons will be made between the treatment groups. Consequently efficacy will only be assessed for Cohort 3. Hence the following analyses apply to Cohort 3 data.

The observed data summaries for all efficacy endpoints, except PGIC, will only use 'on-treatment' records (i.e. on or before the date of last study medication plus 1 day) for all visits, except baseline and follow-up.

For all ANCOVA analyses the treatment least square means (LS means) and LS mean standard errors, treatment difference estimate, standard error, 1-sided p-value, and 90% CI will be presented. The corresponding SAS ANCOVA output will also be outputted for internal statistical review.

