### 6. GENERAL ASPECTS FOR STATISTICAL ANALYSIS

#### 6.1. GENERAL METHODS

All statistical tests for Cohort 3 will be 1-sided at the 0.05 level of significance and accompanied by a 2-sided 90% CI. There will not be any adjustments for multiple comparisons. No statistical testing will be performed with the data from Cohorts 1 and 2.

All summaries and listings will be presented by treatment group and by cohort. For Cohorts 1 and 2, adverse events and pharmacokinetic data will be presented by treatment group and BSA treated (10%, 40% and overall) to assess whether BSA impacts this data.

Only on-treatment records will be summarised for post-baseline visits, except follow-up, unless stated otherwise. A record is considered on-treatment if it is on or before the date of last study medication plus 1 day.

Continuous variables will be summarised using the number of observations (n), mean, standard deviation (SD), 95% Confidence interval (CI) of mean, median, minimum, and maximum. Geometric mean and coefficient of variation (CV) will be included for PK parameters, where appropriate. Categorical variables will be summarised using frequencies and percentages. The number of missing values will be presented in summary tables. The missing count will not include

SAP Version v2.0 Page 22 of 43

Date: 16th March 2017

subjects who have discontinued at earlier visits.

Unless otherwise specified, the estimated mean and median for a set of values should be printed out to 1 more decimal place than the original values, and standard deviations should be printed out to 2 more decimal places than the original values. The minimum and maximum should report the same number of decimal places as the original values. The coefficient of variation will always be reported as a percentage to 1 decimal place. Percentages will be displayed with 1 decimal place; except percentages will not be presented when the count is zero and 100% will be presented as an integer.

Unless stated otherwise, baseline will be defined as the last non-missing measurement prior to administration of the first dose of IMP.

In by-visit summary tables the baseline will be summarised using all available data, but also for each visit using only the baseline data from subjects with available data at the visit; hence the mean change from baseline will equal the mean visit value – mean baseline value.

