### 6.3. VISIT WINDOWS

There is no requirement for visit windows for Cohorts 1 and 2 as subjects will remain in the CRU for the duration of the study, so all assessments will be presented and analysed according to the visit assessment recorded.

For Cohort 3, all assessments will be presented and analysed according to the visit assessment recorded. Due to the short study duration visit windows will not be used. If possible, any early termination visits will be assigned to the closest study visit if they are on-treatment. Prior to database lock the data will be reviewed to identify any outlying visits and make decisions on how to deal with any issues. All decisions will be documented prior to database lock.

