#### 8.1. PRIMARY EFFICACY ENDPOINT AND ANALYSIS

The primary endpoint is the percentage change from baseline to Week 2 in the EASI score. Baseline will be taken as the last non-missing measurement prior to administration of the first dose of IMP, this should be Day 1 for the primary endpoint.

The observed percentage change from baseline to Week 2 in the EASI score will be analysed for the FAS with an Analysis of Covariance (ANCOVA) model that includes baseline score as a covariate and treatment (ZPL521 or placebo). The treatment effect will be estimated with the difference between the least square means (LS means), defined as ZPL521 - placebo.

The ANCOVA analysis assumptions will be checked by evaluating the model residuals. A Shapiro-Wilks test will be performed on the residuals; a p-value > 0.1 will be considered proof of normality. If the Shapiro-Wilks p-value is  $\leq 0.1$ , the residual plot will be evaluated for symmetry. If the evaluation of residuals indicates a problem with the model assumptions, a transformation of the data will be considered, including a rank-transformation of the data.

The EASI score will be summarised by treatment and visit for the FAS with observed data. Summaries will present the descriptive statistics for baseline, change from baseline and percentage change from baseline data.

Patient profile plots by treatment group, of the percentage change from baseline in EASI score will also be presented. Note that only observed data will be included in these plots; i.e. no imputations will be used.

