### 8.2. SECONDARY ENDPOINTS AND ANALYSIS

#### 8.2.1. EASI-50 and EASI-75

The proportion of subjects who achieve an EASI-50 response will be summarised in the FAS with counts and percentages by treatment group at each visit. The number of missing values will also be presented.

An exact logistic regression analysis will be performed at Week 2. The model will include treatment and baseline EASI score. The odds ratio, p-value and associated exact 90% CI will be presented. Subjects with missing responses will be counted as non-responders.

The proportion of subjects who achieve an EASI-75 response will be analysed in the same way as described for the EASI-50.

SAP Version v2.0 Page 29 of 43

Date: 16th March 2017

The cumulative proportion of subjects achieving a  $\ge x\%$  reduction in EASI at Week 2 will be plotted against x, with different lines for each treatment group. Subjects with missing data will be regarded as having the worst change from baseline and labelled as such on the plot. Horizontal reference lines will be drawn that relate to the 0, 25, 50 and 75% reductions in EASI scores.

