### 8.2.3. Investigators Global Assessment (IGA)

IGA will be summarised for the FAS with counts and percentages by treatment at each visit. The number of missing values will also be presented. Shift tables of change from baseline will also be presented with marginal totals.

IGA response will be summarised at each visit with counts and percentages; missing responses will also be tabulated. An exact logistic regression analysis will be performed for Week 2. Baseline IGA, stratification variable (baseline EASI; ≤20 or >20) and treatment will be included in the models as factors; subjects with missing responses will be counted as non-responders. The odds ratio, p-value and associated exact 90% CI will be presented. This analysis will be repeated for IGA success.

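### The SAP's on-treatment cut-off (last dose date + 1 day) drops a Cohort 3 Visit 5 held on Day 16, inside the protocol's ±1 day window, from the Week 2 efficacy and laboratory summaries

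*SAP*

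**What the plan says.** **The cut-off.** SAP 6.1 says: "A record is considered on-treatment if it is on or before the date of last study medication plus 1 day". Apart from follow-up, only such records are summarised after baseline. SAP 8 repeats the rule for efficacy: "The observed data summaries for all efficacy endpoints, except PGIC, will only use 'on-treatment' records", with baseline and follow-up exempt. SAP 10.4 applies the same limit to the laboratory summaries, to the counts of values of potential clinical concern and to the liver-test counts.

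**The visit.** Protocol Section 6 lets Cohort 3 visits fall one day either side of the scheduled day and excepts only screening and follow-up. Protocol Table 3 gives the same margin. Protocol 6.4.3 and the Table 11 footnotes put the last application on the evening of Day 14, before the Day 15 visit. Protocol Table 2 caps dosing at 14 consecutive days.

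**Assignment and models.** SAP 6.3 uses no visit windows: "For Cohort 3, all assessments will be presented and analysed according to the visit assessment recorded". It adds: "Prior to database lock the data will be reviewed to identify any outlying visits", with decisions documented. For the primary analysis SAP 8.1 says: "The observed percentage change from baseline to Week 2 in the EASI score will be analysed for the FAS".

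**Laboratory schedule.** Protocol Table 11 has Cohort 3 safety laboratory tests at screening, baseline, Visit 5 and follow-up.

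**The concern.** The cut-off fits a Visit 5 held exactly on Day 15 and leaves no room for the extra day that the protocol allows. A patient who doses as planned and attends on Day 16 has followed the protocol, yet has no Week 2 entry in the EASI, IGA, NRS, VRS or BSA summaries. If the ANCOVA keeps the record, the descriptive table and the model beside it rest on different patients, and nothing in the SAP tells the reader why.

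The laboratory consequence needs no interpretation, because SAP 10.4 states the limit outright. Visit 5 is the only scheduled Cohort 3 laboratory sample between baseline and follow-up. A Day 16 patient would therefore have no scheduled on-treatment value in the summaries or alert counts, although safety is a secondary objective of this cohort.

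**Working it through.** **1. The plan's own figure.** Inputs from SAP 3.3: 20 active, 10 placebo, difference 30, SD 30, 1-sided 5%.

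- Noncentrality = 30 / (30 × √(1/20 + 1/10)) = 1/0.3873 = 2.58.
- Noncentral-t power = 80.9% with 28 df, or 80.8% with 27 df (one covariate).

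The stated 80% is reproduced. The sample-size statement is not in question.

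**2. The dates.** A record is on-treatment if visit day ≤ last dose day + 1. With the last dose on Day 14 the limit is Day 15.

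| Visit 5 held on | Within protocol ±1 day | Days after last dose | On-treatment |
|---|---|---|---|
| Day 14 | yes | 0 | yes |
| Day 15 | yes | 1 | yes |
| Day 16 | yes | 2 | **no** |

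**3. Do the models use the record?** The text leans clearly towards yes.

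- SAP 8 limits the filter to observed data summaries. Its paragraph on ANCOVA output carries no filter.
- SAP 6.3 has assessments both presented and analysed by recorded visit.
- SAP 8.1 uses the word observed to mean not imputed: "Note that only observed data will be included in these plots; i.e. no imputations will be used".

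The point is not stated outright, and the label Observed Case in the SAP's index of tables is not defined.

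**4. Effect on a summary mean.** If one patient lying 1 SD (30 points) from the mean of all *n* is left out, the mean of the rest moves by 30/(n − 1):

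- placebo: 30/9 = 3.3 points
- active: 30/19 = 1.6 points

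The 1 SD distance is an assumption for illustration.

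**5. Only if the filter also reached the models (the less likely reading).** ANCOVA df = N − 3; 90% CI half-width = t(0.95, N − 3) × 30 × √(1/a + 1/b).

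| Active / placebo | Power | Half-width |
|---|---|---|
| 20 / 10 | 80.8% | 19.8 |
| 19 / 10 | 80.2% | 20.0 |
| 20 / 9 | 78.3% | 20.5 |

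One lost record would cost about 0.7 to 2.6 points of power. In the responder models, one responder recoded as a non-responder would move the placebo rate by 1/10 = 10 points or the active rate by 1/20 = 5 points.

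**The case against.** **A stronger reading that a reader might infer.** SAP 8.2.1 says of the EASI-50 model: "Subjects with missing responses will be counted as non-responders". SAP 8.2.3 says the same for IGA: "subjects with missing responses will be counted as non-responders". One could conclude that a Day 16 record drops out of the primary ANCOVA and that a measured responder becomes a non-responder. The documents do not support this: the filter names summaries only, and SAP 6.3 and 8.1 point to keeping the record. The figures in step 5 of the working should not be cited as the expected cost.

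**A pre-lock review exists.** SAP 6.3 provides for documented decisions on outlying visits, so it would be wrong to say that nobody would look. But a visit inside the protocol window need not count as outlying.

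**The cut-off has a rationale.** Other treatment for atopic dermatitis is permitted from the end of dosing (Protocol 5.11, SAP 3.2). Table 11 also asks for a PK sample about 12 hours after the last dose at Visit 5, whereas a Day 16 morning visit would be about 24 + 12 = 36 hours after an evening dose on Day 14. This supports some limit and a flag on affected records. It does not take Visit 5 out of the ±1 day window.

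**The spare jar.** Protocol 5.5 supplies a spare jar for late visits so that dosing is continuous. If a patient dosed on Day 15, a Day 16 visit would be last dose + 1 day and would be kept. That text sits uneasily with the Day 14 last application and the 14-consecutive-day maximum. The passages must be reconciled.

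**It is small and visible.** Summary tables show *n* and missing counts (SAP 6.1), the laboratory result is still listed with abnormal alerts (SAP 10.4), and follow-up laboratory tests are scheduled. All true. Even so, follow-up comes 7 to 14 days after the last dose and does not replace an end-of-treatment value, and a visible mismatch is still a mismatch.

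**Conclusion.** The concern holds for the summaries. Followed exactly, the SAP excludes a protocol-compliant Day 16 Visit 5 from the Week 2 observed-data summaries of every efficacy endpoint except PGIC. It also excludes it from the laboratory summaries, the potential-clinical-concern counts and the liver-test counts. This assumes a last dose on Day 14, as scheduled.

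The number of patients affected is unknown. Each one could move a Week 2 summary mean by the few points shown above, in a trial whose planned 90% CI half-width is about 20. The effect on the primary ANCOVA is probably nil. The main costs are tables and models that may not describe the same patients, and a missing end-of-treatment laboratory value in the safety tables. The issue is modest, but it comes from a stated rule and is cheap to correct.

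**What to change.** Before database lock, amend SAP 6.1, 8 and 10.4 to state that:

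- a Cohort 3 record labelled Visit 5, taken on Day 15 ± 1 day and no later than the last dose date + 2 days, counts as the on-treatment Week 2 record;
- all other records, including early-termination visits, keep the + 1 day rule;
- the same Week 2 records feed the summaries, the ANCOVA and the responder models;
- this changes only the on-treatment flag, so assignment by recorded visit in SAP 6.3 stands.

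Tie the rule to the last-dose date and not to completion of the treatment period. SAP 7.1 counts completers without defining them, and a completer who missed the final applications could otherwise qualify several days after the last dose (for example, last dose on Day 12 and visit on Day 15, which is + 3 days).

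Flag any such record taken after other treatment for atopic dermatitis was started. Show the + 1 day version as a sensitivity table only if such a record occurs.

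Separately, reconcile the spare-jar text in Protocol 5.5 with the Day 14 last application (Protocol 6.4.3, Table 11) and the 14-consecutive-day maximum (Table 2).

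The cost is a few sentences, one programming flag and at most one extra table. The downside is that a few values may reflect up to one extra day off treatment.
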